## 10.4.4. Urine Drug Screen and Breath Alcohol Testing

Qualitative UDS will be utilized to test for the following drugs of abuse: buprenorphine, methadone, tetrahydrocannabinol, oxycodone and other opioids, methamphetamines, amphetamines, phencyclidine, oxycodone, propoxyphene, cocaine, barbiturates, and benzodiazepines.

Breath alcohol testing will be performed according to the sites' standard operating procedures. If there is any doubt or concern regarding alcohol use, research site staff may request a breath test for alcohol measures at any time during the study.

Tests will be performed at the visits defined in Table 4.

#### **10.4.5. Vital Signs**

Vital signs will consist of oral body temperature (°C), blood pressure (systolic and diastolic blood pressure, mmHg), pulse rate (beats per minute), and respiratory rate (breaths/min) collected while sitting with legs uncrossed and feet flat on floor, following a rest period of at least 3 minutes.

## 10.4.5.1. Qualification Phase Vital Signs Safety Monitoring

Before each scheduled IR morphine 30 mg dose is administered during the Qualification Phase, research or nursing staff will record oxygen saturation and respiratory rate and assess the subject for sedation and/or intoxication. If respiratory rate is <12 breaths per minute or oxygen saturation is <95% (Section 10.4.7), the measurements will be repeated and recorded. If either oxygen saturation or respiratory rate remain outside parameters or the subject appears sedated or intoxicated, the oral IR morphine 30 mg maintenance dose will be withheld and a study Investigator notified. The withheld dose may be administered later (and recorded) once it is determined that the subject's status has returned to within the safety dosing criteria.

After the Qualification/Baseline Hydromorphone Challenge Session, subjects will be assessed based upon the same safety criteria described above (i.e., respiratory rate, oxygen saturation and sedation or intoxication) to determine if it is safe to resume administration of oral IR morphine 30 mg maintenance dosing. This assessment will be documented. In the event that morphine dosing is withheld in the afternoon, evening administration of oral IR morphine 30 mg will be scheduled for no later than the original scheduled administration time in order to maintain consistency between time of last dose of morphine and Hydromorphone Challenge Session dosing the following day.

Version: 2.0, 17NOV2015 Page 62 of 99

## 10.4.5.2. Treatment Phase Vital Signs Safety Monitoring

After each dose of IM hydromorphone during the Treatment Phase Hydromorphone Challenge Sessions, subject's oxygen saturation, respiratory rate, and overall safety profile will be reviewed by the research/nursing staff (as described in Section 7.1.2.1) to determine whether it is safe to proceed with administration of the next dose of hydromorphone.

Vital signs assessments will be performed at the visits and time points defined in Table 4.

#### 10.4.6. 12-Lead Electrocardiograms

12-Lead ECGs will be performed after the subject has been resting in a recumbent/supine position for at least 3 minutes. The ECG variables will include ventricular heart rate and the PR, QRS, QT, and QTcF intervals. The ECGs will be signed and dated by a medically qualified individual to confirm review of the ECG and verify whether any abnormalities are clinically significant. In general, abnormal, clinically significant ECGs are expected to be associated with an item recorded in medical history or with an AE.

Assessments will be performed at the visits and time points defined in Table 4.

#### 10.4.7. Cardiac Monitoring (including Pulse Oximetry)

Cardiac monitoring (cardiac rhythm, heart rate) and pulse oximetry will be performed from inpatient check-in to the end of the Treatment Phase (or Early Termination) of the study. Data will not be recorded in the database, but will be used for real-time safety monitoring. Occurrences of oxygen saturation <95%, the measurements will be repeated and recorded as AEs. Pulse oximetry/cardiovascular monitoring will be included on each Hydromorphone Challenge Session day (i.e., Day -3, -2, -1, 1, 2, 3, 4, 5, 6, 8, 9, 10, 11, 12, and 13). Monitoring will be from pre-dose until at least 5 hours post-dose or longer, if clinically indicated. Cardiac monitoring and pulse oximetry equipment may be removed briefly (for hygiene purposes), as needed.

Continuous pulse oximetry and telemetry can be performed if the Investigator deems it is necessary.

#### 10.4.8. Physical Examination

A complete physical examination including all major body systems will be performed at Screening. At select subsequent study visits, an abbreviated review of systems will be performed to capture changes since Screening.

Height, weight and BMI will be assessed as described in Table 4.

#### 10.4.9. Injection Site Examination

CAM2038 injection sites will be examined daily, after each injection, during the Treatment Phase for any signs of adverse site reactions. The injection site will be visually inspected daily for evidence of erythema, edema, itching, pain, infection, bleeding, abnormal healing and any other abnormalities. Injection sites will be examined daily after each injection to determine if any site related adverse reactions have occurred.

Version: 2.0, 17NOV2015 Page 63 of 99

## 10.4.10. Clinical Opiate Opioid Withdrawal Scale (COWS)

The COWS contains 11 physically observable signs, rated present or absent, based on a timed period of observation of the patient by a rater. This scale is a valid and reliable indicator of the severity of opiate withdrawal over a wide range of common signs and symptoms (Appendix 17.2; Wesson, 2003).

#### 10.4.11. Objective Opioid Withdrawal Scale (OOWS)

The Objective Opioid Withdrawal Scale (OOWS) contains 13 physically observable signs, rated present or absent, based on a timed period of observation of the patient by a rater (Appendix 17.3; Handelsmen et. al. 1987).

#### 10.4.12. Columbia-Suicide Severity Rating Scale

The C-SSRS will be used to assess both behavior and ideation that tracks all suicidal events, and provides a summary of suicidal ideation and behavior. It assesses the lethality of attempts and other features of ideation (frequency, duration, controllability, reasons for ideation, and deterrents), all of which are significantly predictive of completed suicide.

Two versions of the C-SSRS will be used in this study: the Baseline/Screening version (6 months and lifetime history; Appendix 17.4) and the Since Last Visit version (Appendix 17.5). The Screening version of the C-SSRS will be administered at Screening. The Since Last Visit version of the C-SSRS will be administered at all subsequent assessment times, as indicated in Table 4, by the Investigator or his/her qualified designee (qualified designee is defined as someone that has completed the C-SSRS training within the last 2 years). The survey should be administered by the same assessor, where possible, throughout the study.

#### 10.4.13. Montgomery-Asberg Depression Rating Scale (MADRS)

The Montgomery-Asberg Depression Rating Scale (MADRS) will be used to assess subjects for the presence of symptoms that are most frequently observed in patients with major depression. The scale will be conducted as a clinical interview in which subjects will be required to respond to 10 questions. The items will be rated with regards to how the patient has done over the past week (Appendix 17.6; Montgomery, 1979).

# 10.5. Appropriateness of Measures

As the primary objective of this study is to demonstrate CAM2038 q1w-induced blockade of hydromorphone effects; Drug Liking VAS has been chosen as the primary pharmacodynamic variable.

The Drug Liking VAS assesses the response to the question "At this moment, I like this drug." Values for this scale range from 0 ("Strong disliking") to 100 ("Strong liking"), with 50 as the neutral point ("Neither like nor dislike"). This scale has been included to understand the time course of CAM2038 q1w-induced blockade of subjective effects of hydromorphone. Additional subjective effects VASs will be collected to support findings on the primary measure. The subjective effects VAS items will measure positive (Good Drug Effects and High), negative (Bad

Version: 2.0, 17NOV2015 Page 64 of 99

Drug Effects), and other subjective effects (Any Drug Effects, Desire to Use Opioids, and Alertness/Drowsiness VAS) to further assess the pharmacologic response to the Hydromorphone Challenge Session injection.

Pharmacokinetic measures are included to confirm exposure, explore potential relationships between pharmacokinetic and subjective measures, and if necessary, to aid in the interpretation of unusual responses.

Standard safety outcomes, such as AEs, ECG, vital signs and clinical laboratory testing will be assessed during the study. In addition, respiratory rate and oxygen saturation safety monitoring will be included prior to dosing with IR morphine 30 mg and after dosing with hydromorphone.

# 10.6. Additional Safety Measures and Withdrawal

#### 10.6.1. Opioid Effects

Buprenorphine and hydromorphone can produce the typical side effect profile of mu opioid agonists, and these may include nausea, vomiting, headache, dry mouth, itchiness, drowsiness, sweating, dizziness, stimulation, somnolence, lightheadedness, restlessness, a feeling of well-being, talkativeness, urinary retention and constipation. More serious side effects may include allergic reaction and respiratory depression. However, subjects will be opioid-dependent and, thus, familiar with these common side effects, and not likely to experience the severe side effects such as allergic reaction.

Physiological and behavioral effects, as well as the emergence of possible side effects, will be monitored daily during Hydromorphone Challenge Sessions. Subjects who exhibit hypersensitivity (i.e., experience a SAE) following administration of any of the drugs will be excluded from further research participation. Heart rate, blood pressure, oxygen saturation and respiratory rate will be monitored frequently throughout sessions. However, if a subject experiences an allergic reaction, diphenhydramine will be available for oral administration.

While the risk of significant respiratory depression may be decreased in opioid-dependent individuals (due to greater tolerance), standardized criteria for nursing staff and research personnel will be employed during the monitoring of individuals. If respiratory rate drops below 12 breaths/min accompanied by sedation, subjects will be prompted verbally to breathe. This approach of physical and verbal stimulation is often sufficient to prompt breathing and restore a normal respiratory rate. Subjects will be monitored carefully with a watch-and-wait approach and will be accompanied continuously by nursing personnel and evaluated by the staff physician. If clinical evaluation determines that a subject's level of sedation is increasing, naloxone will be promptly administered parenterally to produce immediate reversal of the hydromorphone effects. Naltrexone will also be available if longer blockade is necessary.

The study will be conducted in CRUs with trained nursing staff available on site. A crash-cart with naloxone will be on site as well. Emergency response will be available by a physician codeteam if needed.

Version: 2.0, 17NOV2015 Page 65 of 99

#### 10.6.2. Treating Opioid Withdrawal

If opioid withdrawal occurs after dosing with CAM2038 q1w (precipitated withdrawal), the following assessments will be collected every 4 hours while the subject is awake for at least 24 hours after dosing to include:

- 1) COWS,
- 2) OOWS,
- 3) VAS assessment of opioid withdrawal severity.

Treatment will be based upon clinical judgment of the medically responsible physician at each site. To ensure the safety of subjects, incidences of precipitated withdrawal in response to CAM2038 q1w will be followed carefully and an amendment of the protocol to ensure subjects are in a more advanced state of opioid withdrawal e.g., increase required COWS score from 8 to 12, to reduce the risk of BPN-related precipitated withdrawal, will be considered if more than one incidence occurs.

Ancillary medications that will be made available for symptomatic relief of all episodes of withdrawal (precipitated by CAM2038 q1w and other) are summarized in Table 5Error!

Reference source not found. Error! Reference source not found.

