#### 7.1.3. Treatment Phase

#### 7.1.3.1. Days 0 to 6

On the morning of Day 0 of the Treatment Phase, subjects will receive one of the following treatments (based on randomization in a 1:1 ratio, stratified by gender) to:

- Group A: CAM2038 q1w 24 mg SC injection
- Group B: CAM2038 q1w 32 mg SC injection

Maintenance IR morphine 30 mg will be withheld for at least 12 hours prior to CAM2038 q1w dosing; therefore, the Day -1 evening dose and the Day 0 morning dose of IR morphine 30 mg will be withheld. The Clinical Opiate Withdrawal Scale (COWS; See Section 17.2) will be administered prior to dosing with CAM2038 q1w; in order to be dosed on Day 0, subjects will be required to have a COWS score of  $\geq 8$ , indicative of mild withdrawal.

CAM2038 q1w treatment will be administered at approximately 9:00 am; CAM2038 q1w administration instructions for user (IFU) will be provided in the Manual of Procedures (MOP).

On Days 1 to 3 and Days 4 to 6, subjects will undergo 2 separate Hydromorphone Challenge Sessions (described in Section 7.1.4), with each daily challenge dose of IM hydromorphone administered at approximately 9:00 am (i.e., approximately 24, 48, 72, 96, 120, and 144 hours following Day 0 CAM2038 q1w injection). Safety and pharmacodynamic assessments will be conducted immediately following each dose of hydromorphone administered in each Hydromorphone Challenge Session (maximum 5 hours after Hydromorphone Challenge Session). Plasma samples will also be collected prior to hydromorphone dosing on each day of the Hydromorphone Challenge Sessions.

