Hydromorphone Challenge Session x				X		X		X		

<sup>q Any spontaneously reported adverse events will be recorded after the subject signs the informed consent form.

Version: 2.0, 17NOV2015 Page 39 of 99

<sup>r C-SSRS (since last visit) will be administered on Day -4, prior to dosing with CAM2038 q1w on Day 0 and Day 7, and prior to discharge on Day 14/ET.

<sup>s MADRS will be administered at Screening, Day -4, prior to dosing with CAM2038 q1w on Day 0 and Day 7, and prior to discharge on Day 14/ET.

<sup>t COWS will be administered on each CAM2038 q1w dosing day, prior to dosing. In order to be dosed on Day 0, subjects must have a COWS score ≥ 8. If opioid withdrawal occurs after dosing with CAM2038 q1w (precipitated withdrawal), COWS and OOWS will be collected every 4 hours while the subject is awake for at least 24 hours after dosing. COWS and OOWS will be administered prior to dosing on each Hydromorphone Challenge Session day.

<sup>u COWS and OOWS will be administered prior to dosing on each Hydromorphone Challenge Session and as needed, if a subject experiences precipitated withdrawal following administration of CAM203 q1w.

Very Subjects will be given a short-acting oral opioid, IR morphine 30 mg, QID, for a minimum of 3 days and a maximum of 7 days prior to the Qualification/Baseline Hydromorphone Challenge Session. One additional dose of IR morphine 30 mg may be administered for the first 3 days of stabilization, as needed, at the investigator's discretion. Subjects will not receive their dose of oral IR morphine 30 mg for approximately 12 hours prior to dosing with CAM2038 q1w on Day 0.

w Subjects will be dosed with either CAM2038 q1w 24 mg or 32 mg SC injection depending on the subject's treatment group assignment. A second dose of CAM2038 q1w will be administered on Day 7.

x Subjects will be scheduled to receive 3 doses of hydromorphone (0 mg [Placebo], 6 mg, and 18 mg) in a randomized crossover manner over 3 consecutive days.

	Screening	Inpatient Qualification Phase			Inpatient Treatment Phase					Follow-up Phone Call
Visit:	1				2					
Day:	-39 to -11	-10, -9, -8, -7, OR -6		-3 to -1	0	1 to 3 & 4 to 6	7	8 to 10 & 11 to 13	14/ ET	21
Pharmacokinetic sampling					Xy	X z	$X^{y}$	X z	Xaa	
Pharmacodynamic training/practice		Xbb								
VAS cc				X		X		X		

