Severity of Opioid Withdrawal VAS					X dd		X			
Check-in		X								
Discharge									Xee	

BMI=body mass index; COWS=Clinical Opiate Withdrawal Scale; C-SSRS=Columbia-Suicide Severity Rating Scale; DSM-V = Diagnostic and Statistical Manual of Mental Disorders – Fifth Edition; ECG=electrocardiogram; ET=Early Termination; FSH=Follicle Stimulating Hormone; HIV= Human Immunodeficiency Virus; MADRS=Montgomery-Asberg Depression Rating Scale; OOWS=Objective Opioid Withdrawal Scale; PD=pharmacodynamic VAS=visual analog scale.

- y Blood samples will be taken pre-dose and 1, 4, 6 and 8 hours after CAM2038 q1w injection
- z Blood samples will be taken approximately 60 minutes prior to administration of hydromorphone on each of the 3 Hydromorphone Challenge Session days during the Treatment Phase (i.e., Days 1, 2, 3, 4, 5, 6, 8, 9, 10, 11, 12, and 13).
- aa Blood samples will be taken approximately 168 hours after CAM2038 q1w injection
- bb Pharmacodynamic training may be administered as frequently as required, but all subjects must complete at least one training session prior to the Qualification/Baseline Hydromorphone Challenge Session. Training can only occur prior to or after, but not during the Hydromorphone Challenge Sessions.
- cc On Hydromorphone Challenge Session days (i.e., Day -3, -2, -1, 1, 2, 3, 4, 5, 6, 8, 9, 10, 11, 12, and 13), subjective measures (Drug Liking, Feeling High, Any Drug Effects, Good Drug Effects, Bad Drug Effects, Sedated, Desire to Use Opioids VAS) assessments will be performed at predose (up to 15 minutes prior to dosing) and at 5, 10, 15, 30, 45, 60, 75, 90, 120, 150, 180, 210, 240, 270 and 300 minutes post-dose.
- dd Severity of Opioid Withdrawal VAS will be administered, as needed, if a subject experiences precipitated withdrawal following administration of CAM203 q1w.
- ee Subjects will be discharged on Day 14, if medically acceptable.

Version: 2.0, 17NOV2015 Page 40 of 99

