Many studies have evaluated the conditions under which buprenorphine can be administered to opioid dependent individuals to avoid the precipitation of withdrawal. Collectively, these studies have shown that BPN-precipitated withdrawal is dependent on the following: 1) duration of action of the maintenance opioid (whereby precipitated withdrawal is more likely to occur in those maintained on long-acting opioids (e.g., methadone) than short-acting opioids (e.g., heroin), 2) the time since last opioid maintenance dose (whereby precipitated withdrawal is more likely to occur when opioid dosing is recent and more opioid is on board than when time for opioid wash-out has occurred and the individual is showing signs of opioid withdrawal, and 3) the absolute dose of BPN (whereby a higher BPN dose is more likely to precipitate withdrawal compared to a lower dose of BPN). The strategy proposed here addressed each of these principles in the following manner: 1) Subjects will be maintained on a short-acting opioid, morphine, rather than a long-acting opioid, 2) Morphine will be omitted for a period of ~12 hours and withdrawal signs and symptoms are expected to emerge during this interval prior to CAM2038 q1w administration (subjects will be required to score 8 points or greater on the COWS prior to being dosed with CAM2038 glw on Day 0 (Walsh et al., 2015), and 3) while the absolute depot dose of CAM2038 q1w at 24 and 32 mg is high, the more relevant factor is the initial concentration exposures following the injection and the rate of onset, whereby a slower rate of BPN delivery is associated with decreased likelihood of precipitated withdrawal (Rosado et al., 2007). The standard recommended approach (although not necessarily the most commonly used in clinical practice) is to begin dosing with 4 mg, wait for 2 hours and, in the absence of precipitated withdrawal, administer an additional 4 mg. A 4 mg sublingual tablet of BPN will produce a concentration of approximately 2 ng/mL (Cmax) at approximately 1 hour post-dose (Ciraulo et al., 2006), while an 8 mg initial dose would produce ~4.3 ng/mL (Cmax) at approximately 1.5 hour post-dose (HS-11-426). With respect to the CAM2038 q1w doses proposed for testing here, even at the highest dose (32 mg), BPN plasma levels will not exceed 2 ng/mL until approximately ~4 hours after administration. Thus, the initial BPN concentration exposure is predicted to be lower than the exposure typically seen during the first 2-4 hours of initial induction with SL products. Moreover, with CAM2038 q1w, concentrations will continue to slowly rise, reaching Cmax at approximately 24 hours post-dose. While BPN-precipitated withdrawal is a relatively rare occurrence in clinical practice, one strategy employed for treatment is to give more BPN. Given the pharmacokinetics of CAM2038 q1w, this potential approach for treating BPN-precipitated withdrawal is built into the product design and may serve to ameliorate any potential withdrawal effects. However, if withdrawal does occur, specific procedures have been included to ensure that subjects are assessed and receive treatment for symptoms (See Section 10.6).

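### On Day 0 no withdrawal scale is scheduled for all subjects between the first CAM2038 injection and the Day 1 score about 24 hours later, so mild to moderate worsening can go unscored

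*Protocol*

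**What the plan says.** **Entry state.** Protocol 7.1.3.1 states that "in order to be dosed on Day 0, subjects will be required to have a COWS score of" 8 or more. Section 7.2 explains that morphine is withheld for about 12 hours and that "withdrawal signs and symptoms are expected to emerge during this interval prior to CAM2038 q1w administration".

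**Scheduled scores.** Table 4 footnote t says "COWS will be administered on each CAM2038 q1w dosing day, prior to dosing". COWS and OOWS are next due for everyone before the hydromorphone dose on each challenge day, the first being Day 1. Footnote u, attached to the Day 0 COWS and OOWS cells, adds scoring "as needed, if a subject experiences precipitated withdrawal following administration of CAM203 q1w". Day 0 is not a challenge day, so footnote u does not clearly provide a pre-dose OOWS. Footnote dd reads "Severity of Opioid Withdrawal VAS will be administered, as needed, if a subject experiences precipitated withdrawal", so the severity VAS has no assured pre-injection value.

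**Conditional scores.** Section 10.6.2 begins "If opioid withdrawal occurs after dosing with CAM2038 q1w (precipitated withdrawal), the" and then calls for COWS, OOWS and the severity VAS every 4 waking hours for at least 24 hours. Raising the entry COWS from 8 to 12 by amendment "will be considered if more than one incidence occurs".

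**Adverse events.** Section 10.4.1.1 excludes withdrawal symptoms from the adverse event form because dedicated assessments are meant to record them.

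**Other Day 0 contacts.** Footnote p schedules vital signs to 6 hours. Footnote y states: "Blood samples will be taken pre-dose and 1, 4, 6 and 8 hours after CAM2038 q1w injection".

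**The concern.** Leaving withdrawal out of the adverse event data is reasonable only if the dedicated scales are applied when withdrawal is most likely to change. After the first injection they are not applied to everyone. A site must first decide that buprenorphine has precipitated withdrawal in someone who was already in withdrawal, and only then does it start the measurements that would inform that decision.

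A marked reaction would probably be noticed in an inpatient unit. A modest rise from an entry score of 8 or 9 might not be labelled, and would then leave no score. Two things are at stake. One is the stated safety and tolerability objective as it applies to induction at 24 mg and 32 mg. The other is the count in 10.6.2 that prompts the sponsor to reconsider the entry threshold, because sites that label more or less readily would contribute differently to it.

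**Working it through.** The plan gives no incidence of precipitated withdrawal, so there is no figure to reproduce. The check compares the schedules and adds some simple arithmetic.

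**1. Day 0 contacts after the injection (about 9:00), for all subjects (Table 4, footnotes p, t, u, y, dd)**

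| Assessment | Times after injection | Number |
|---|---|---|
| Vital signs | 15, 30, 60 min; 2, 3, 4, 5, 6 h | 3 + 5 = 8 |
| Blood draws | 1, 4, 6, 8 h | 4 |
| COWS | none unless precipitated withdrawal is judged present | 0 |
| OOWS | none unless precipitated withdrawal is judged present | 0 |
| Severity VAS | none unless precipitated withdrawal is judged present | 0 |

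The next COWS and OOWS for everyone precede the Day 1 challenge at about 9:00, so the gap is about 24 h.

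**2. How much of the buprenorphine rise falls in the gap** (Protocol Table 1, 32 mg, geometric means, as a share of the 24 h level of 5.00 ng/mL)

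- 1 h: 0.391 / 5.00 = 8%
- 4 h: 1.83 / 5.00 = 37%
- 6 h: 2.61 / 5.00 = 52%
- 8 h: (2.61 + 4.42) / 2 = 3.515, and 3.515 / 5.00 = 70%. This assumes linear interpolation between the 6 h and 10 h values.

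Scores at the existing draws would follow much of the rise. These are exposures in healthy subjects under naltrexone, not withdrawal rates.

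**3. Why the Day 1 score is not a full substitute** (Protocol 9.7 and Table 5)

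Ancillary withdrawal medication is barred from midnight before the Day 0 injection. It is then allowed from the injection until midnight, 9:00 to 24:00 = 15 h, and barred again for the 9 h before the Day 1 score. The Day 1 score can therefore follow symptomatic treatment that the Day 0 pre-dose score did not.

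**4. Room for unlabelled worsening** (Appendix 17.2)

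The form's mild band is 5 to 12 and its moderate band starts at 13. A subject at the minimum entry score can rise by 12 - 8 = 4 points without leaving the mild band, and needs 13 - 8 = 5 points to reach moderate.

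**5. How a threshold of two responds to recognition (illustration only)**

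Let q be the share of subjects who truly worsen because of CAM2038, and s the share of those whom sites label. Both are assumptions. With 48 subjects (the planned number of completers), independent cases and no false labels, put p = q × s. Then P(at least 2 labelled) = 1 - (1 - p)^48 - 48p(1 - p)^47.

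| q | s = 100% | s = 50% | s = 25% |
|---|---|---|---|
| 5% | 0.70 | 0.34 | 0.12 |
| 10% | 0.96 | 0.70 | 0.34 |
| 20% | 1.00 | 0.96 | 0.70 |

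At q = 5%, halving recognition roughly halves the chance of reaching the trigger. At q = 20%, it hardly matters.

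**6. What the planned reports would show**

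SAP Appendix A lists 8 change-from-baseline tables for COWS and OOWS: 4 in the Completer Population and 4 in the ITT Population. Listing 16.2.6.1 gives subject-level scores. All can show only scores that were taken.

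**The case against.** A reader might infer that 10.6.2 counts any withdrawal still present after the injection, so that ordinary continuing morphine withdrawal would be a case. The section does not support that. It goes on to speak of withdrawal that is a response to CAM2038 and of buprenorphine-related cases, and it separates episodes that CAM2038 brings on from other episodes. Attribution is left to clinical judgment in a staffed inpatient unit, which is a defensible choice.

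Other parts of the defence also stand. The ITT tables and Listing 16.2.6.1 would carry nearly all scores that are taken, so the absence of a Safety Population table loses little. SAP 6.1 allows averaging of baseline scores, but Protocol 12.3 takes the last assessment before first dosing. If study medication there means CAM2038, that is already the Day 0 pre-dose COWS. Drug treatments and the reasons for them are recorded (Protocol 9.2.2), and Table 5 medication is available for any withdrawal episode, so care does not depend on the label. Section 7.2 also argues that the slow buprenorphine rise makes precipitated withdrawal less likely.

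It is fair, too, that extra Day 0 scores would be affected by ancillary medication and that the physician would still attribute cause. Neither answers the remaining gap. A subject whose worsening is not labelled has no score at all for about 24 h, and no table or listing can recover it.

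**Conclusion.** The point holds as a modest gap in safety measurement. On Day 0 all subjects are injected while in withdrawal, no withdrawal scale is applied to all of them for about 24 h afterwards, and the adverse event record is not a backup. Mild to moderate worsening can go unscored, and the count behind the more-than-one-case consideration depends partly on site recognition.

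The size of the effect on that count cannot be estimated from the documents, and the probabilities above rest wholly on assumed rates. The conclusion rests on reading footnotes t, u and dd as written and on sites doing no unscheduled scoring.

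Three stronger readings are not supported. The trigger is not a stopping rule: it only leads to an amendment being considered, and the sponsor may amend without it. The overlap with existing withdrawal does not extend to Day 7, because the COWS requirement of 8 applies only to Day 0. The primary Drug Liking endpoint and its analysis are not affected.

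**What to change.** In Table 4 (footnotes t, u and dd) and Section 10.6.2 of the protocol:

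1. Schedule COWS for all subjects on Day 0 at the existing 1, 4, 6 and 8 h blood draws. Keep the 4-hourly series for subjects judged to have precipitated withdrawal.
2. State that OOWS and the withdrawal severity VAS are also recorded before the injection on Day 0, so that any later score has a reference.
3. State that attribution to CAM2038 stays with the physician, informed by the change from the subject's own pre-dose score. A numeric case threshold is optional. If one is wanted, the sponsor and investigators should set it before the first dose.

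In the SAP, add one summary of change from the Day 0 pre-dose COWS at each time, by CAM2038 dose, for all dosed subjects, noting ancillary medication taken before each score.

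The cost is amendment wording, one added summary, and a few minutes of existing staff time per subject at four contacts already scheduled.
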